9.1.2. Method of Detecting AEs and SAEs

Care will be taken not to introduce bias when detecting AE and/or SAE. Open-ended and non-leading verbal questioning of the participant is the preferred method to inquire about AE occurrence.

9.1.3. Follow-up of AEs and SAEs

After the initial AE/SAE report, the investigator is required to proactively follow each participant at subsequent visits/contacts. All SAEs will be followed until the event is resolved, stabilized, otherwise explained, or the participant is lost to follow-up (as defined in Section 8.3). Further information on follow-up procedures is given in [Appendix 4](#).

9.1.4. Regulatory Reporting Requirements for SAEs

- Prompt notification by the investigator to the sponsor of a SAE is essential so that legal obligations and ethical responsibilities towards the safety of participants and the safety of a study treatment under clinical investigation are met.
- The sponsor has a legal responsibility to notify both the local regulatory authority and other regulatory agencies about the safety of a study treatment under clinical investigation. The sponsor will comply with country-specific regulatory requirements relating to safety reporting to the regulatory authority, IEC, and investigators.
- Investigator safety reports must be prepared for suspected unexpected serious adverse reactions (SUSAR) according to local regulatory requirements and sponsor policy and forwarded to investigators as necessary.
- An investigator who receives an investigator safety report describing a SAE or other specific safety information (e.g., summary or listing of SAE) from the sponsor will review and then file it along with the Investigator's Brochure (IB) and will notify the IEC, if appropriate according to local requirements.

9.1.5. Pregnancy

- Details of all pregnancies in female partners of male participants will be collected after the start of study treatment and until the follow-up visit.
- If a pregnancy is reported, the investigator should inform GSK within 24 hours of learning of the pregnancy and should follow the procedures outlined in [Appendix 5](#).
- Abnormal pregnancy outcomes (e.g., spontaneous abortion, fetal death, stillbirth, congenital anomalies, ectopic pregnancy) are considered SAE.

9.2. Treatment of Overdose

For this study, any dose of Pyrimethamine greater than 50 mg within a 24-hour time period will be considered an overdose.

GSK does not recommend specific treatment for an overdose.

In the event of an overdose, the investigator should:

1. Contact the Medical Monitor immediately.
2. Closely monitor the participant for AE/SAE and laboratory abnormalities until Pyrimethamine can no longer be detected systemically (at least 22 days).
3. Obtain a plasma sample for PK analysis within 22 (\pm 1) days from the date of the last dose of study treatment if requested by the Medical Monitor (determined on a case-by-case basis).
4. Document the quantity of the excess dose as well as the duration of the overdosing in the CRF.

Decisions regarding dose interruptions or modifications will be made by the investigator in consultation with the Medical Monitor based on the clinical evaluation of the participant.

9.3. Safety Assessments

Planned time points for all safety assessments are provided in the SoA.

9.3.1. Physical Examinations

- A physical examination will include, at a minimum, assessments of the Skin, Cardiovascular, Respiratory, Gastrointestinal and Neurological systems.
- Height and weight will also be measured and recorded only at screening.
- Investigators should pay special attention to clinical signs related to previous serious illnesses.

9.3.2. Vital Signs

- Oral temperature, pulse rate, and blood pressure will be assessed.

- Blood pressure and pulse measurements will be assessed with a completely automated device. Manual techniques will be used only if an automated device is not available.
- Blood pressure and pulse measurements should be preceded by at least 5 minutes of rest for the participant in a quiet setting without distractions (e.g., television, cell phones).
- Single vital signs will be measured in a semi-supine position after 5 minutes rest and will include temperature, systolic and diastolic blood pressure, and pulse rate.

9.3.3. Electrocardiograms

- Single 12-lead ECG will be obtained as outlined in the SoA (see Section 2) using an ECG machine that automatically calculates the heart rate and measures PR, QRS, QT, and QTc intervals. Refer to Section 8.1 for QTc withdrawal criteria and additional QTc readings that may be necessary.

9.3.4. Clinical Safety Laboratory Assessments

- Refer to [Appendix 2](#) for the list of clinical laboratory tests to be performed and to the SoA for the timing and frequency.
- The investigator must review the laboratory report, document this review, and record any clinically relevant changes occurring during the study in the AE section of the CRF. The laboratory reports must be filed with the source documents.
- All laboratory tests with values considered clinically significantly abnormal during participation in the study should be repeated until the values return to normal or baseline or are no longer considered significantly abnormal by the investigator or medical monitor.
- If such values do not return to normal/baseline within a period of time judged reasonable by the investigator, the etiology should be identified and the sponsor notified.
- All protocol-required laboratory assessments, as defined in [Appendix 2](#), must be conducted in accordance with the laboratory manual and the SoA.
- If laboratory values from non-protocol specified laboratory assessments performed at the institution's local laboratory require a change in participant management or are considered clinically significant by the investigator (e.g., SAE or AE or dose modification), then the results must be recorded in the CRF.

9.4. Pharmacokinetics

- Whole blood samples of approximately 2 mL will be collected in EDTA blood collection tube for measurement of plasma concentrations of Pyrimethamine as specified in the SoA. Instructions for the collection and handling of biological samples will be provided by the sponsor. The actual date and time (24-hour clock time) of each sample will be recorded.

10. STATISTICAL CONSIDERATIONS

The objectives of this study are to evaluate safety and tolerability of Pyrimethamine and to estimate Pyrimethamine PK parameters in healthy Japanese and Caucasian male subjects. No formal statistical hypotheses will be tested. Descriptive statistics will be used to assess safety and tolerability objectives by group. An estimation approach will be used to address the PK study objectives, where point estimates and corresponding 95% confidence intervals (CI) will be constructed, unless otherwise stated.

10.1. Sample Size Determination

10.1.1. Sample Size Assumptions

The sample size is based on feasibility where sufficient subjects will be enrolled into the study to support the inclusion of 12 evaluable subjects for analysis and 6 subjects are assigned to each group (Japanese or Caucasian).

Between-subject estimates of variability of the PK endpoints C_{max} and AUC(0-inf) of Pyrimethamine are estimated to be 18.1% (coefficient of variance, CV%) and 44.6% (CV%), respectively (based on Japanese PK data reported by [Otomo H, et al. 1985](#)). Based on these variability estimates, and a sample size of 6 (active treatment per group), the upper and lower bounds of 95% CI will be approximately 20.7% for C_{max} and 56.4% for AUC(0-inf) respectively. For instance, the 95% CI of geometric mean will be 331.3-483.0 if the geometric mean of C_{max} (ug/mL) is 400, and the 95% CI of geometric mean will be 25.6-62.5 if the geometric mean of AUC(0-inf) (ug·hr/mL) is 40.

10.1.2. Sample Size Sensitivity

Based on sample size of 6, if the between-subject CV_b% observed in the C_{max} is 10% (CV_b%;19.9%) and 20% (CV_b%;21.7%) greater than between-subject CV_b% in the reference report, the precision estimate for the upper limit value and lower limit value of a mean of 95% CI will be 23.0% and 25.3%, respectively.

If the between-subject CV_b% observed in the AUC is 10% (CV_b%;49.1%) and 20% (CV_b%;53.5%) greater than between-subject CV_b% in the reference report, the precision estimate for the upper limit value and lower limit value of a mean of 95% CI will be 62.8% and 69.3%, respectively.

10.2. Populations for Analyses

For purposes of analysis, the following populations are defined:

Population	Description
Screened	Consisting of all participants screened in the study.
Screening Failure	Participants who sign the ICF in the study but are never subsequently administered. All participants who sign the ICF have

	the screening test in the study.
Safety	All participants who take at least one dose of study treatment.
Pharmacokinetic	This population is defined as all participants administered at least one dose of study treatment and who have PK sample taken and analyzed.

10.3. Statistical Analyses

The study results will be presented in tabular and/or graphical format and summarised descriptively. These analyses will be performed in each group. Complete details of the planned statistical analyses will be provided in the RAP.

10.3.1. Safety Analyses

All safety analyses will be performed on the Safety Population.

Statistical Analysis Methods
AE, clinical laboratory values, vital signs, ECG will be summarized by group.

10.3.2. Pharmacokinetic Analyses

All PK analyses will be described in the PK Population. The details of the PK analysis will be provided in the RAP.

Statistical Analysis Methods
Pyrimethamine concentrations
Plasma concentrations of Pyrimethamine at each assessment point will be listed to prepare figures showing individual concentration-time profiles on both linear and semi-log scales. In addition, the mean and median plasma concentrations at each assessment point will be calculated from concentration data of individual subjects to prepare figures showing mean and median plasma concentration-time profiles on both linear and semi-log scales by group.
Pyrimethamine PK parameters
The PK parameters [i.e., C _{max} , AUC(0-t), AUC(0-inf), AUC(0-24), t _{max} , t _{1/2} , CL/F, V _d /F] will be calculated by non-compartmental analysis from plasma Pyrimethamine concentration-time data using Phoenix WinNonlin (version 6.3 or higher), as data permit. Calculations will be based on the actual sampling times recorded during the study. All derived parameters will be listed and summarized descriptively by each group.

Others

An exploratory analysis will be performed using PK parameter plots in order to assess the results in the Japanese and Caucasian subjects.

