5.4. Scientific Rationale for Study Design

The PK of Pyrimethamine has been investigated following administration of Sulfadoxine/Pyrimethamine tablet (Fansidar[®]) in healthy Japanese subjects [Otomo H, et al. 1985]. However, this study did not include sufficient information for approval of Pyrimethamine in Japan. Confirmation of the PK of Pyrimethamine in a Japanese population, as well as comparison of the data in Japanese relative to Caucasian subjects under the same conditions should be beneficial when confirming the relevance of the existing global experience with Pyrimethamine for patients in Japan.

Daily therapeutic doses of Pyrimethamine have been shown to depress haematopoiesis in some 25% to 50% of patients. The likelihood of inducing leucopenia, anaemia or thrombocytopenia is reduced by concurrent administration of calcium folinate. In addition, PMDA recommends using calcium folinate in this study to be conducted in the healthy subjects. Calcium folinate 15 mg will be dosed from Day 1 to Day 8 to prevent bone marrow depression.

The elimination half-life was approximately 107 hours after dosing 50 mg Pyrimethamine (i.e., two Sulfadoxine/Pyrimethamine (500 mg/25 mg) tablets in healthy Japanese subjects and the mean elimination half-life is reported to be approximately 90 hours in non-Japanese subjects. Considering the long half-life of Pyrimethamine, the follow-up period for 22 days together with the parallel study design are considered to be appropriate for evaluation of the PK characteristics of Pyrimethamine in both Japanese and Caucasian subjects, as well as the evaluation of safety in Japanese subjects because this is the first clinical study of this Pyrimethamine formulation in Japanese.

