	• Plasma concentration time data for Pyrimethamine will be analyzed by non-compartmental methods using Phoenix WinNonlin (version 6.3 or higher) and all derived PK parameters will be graphically presented, summarised and listed. No formal statistical analyses will be conducted.
Safety Analyses	Safety data will be presented in tabular and/or graphical format and summarised descriptively.

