2. SUMMARY OF KEY PROTOCOL INFORMATION

2.1. Changes to the Protocol Defined Statistical Analysis Plan

There were no changes or deviations to the originally planned statistical analysis specified in the protocol (Dated: 19/JUL/2017).

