8.3.2. Summary of Pharmacokinetic Parameters

- For each of these parameters, except for tmax, the following summary statistics will be calculated for each treatment:
 - o Non-transformed: median, maximum, minimum, arithmetic mean, 95% confidence interval for the arithmetic mean and standard deviation
 - Loge-transformed: geometric mean, 95% confidence interval for the geometric mean, standard deviation of logarithmically transformed data and between geometric coefficient of variation (CVb (%))
- For tmax, median, maximum, minimum, arithmetic mean, standard deviation and 95% Confidence Interval (CI) for the arithmetic mean will be calculated.
- An exploratory analysis will be performed using PK parameter plots in order to assess the results in Japanese and Caucasian subjects. Plots of AUC(0-t), AUC(0-inf), Cmax and T1/2 versus group (Japanese, Caucasian) will be produced.

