10.9.6. Pharmacokinetic Tables

Pharma	Pharmacokinetic : Tables					
No.	Population	IDSL / TST ID / Example Shell	Title	Programming Notes	Deliverable [Priority]	
3.1.	PK	PK01: PKCT1	Summary of Pyrimethamine Plasma Concentration		SAC [1]	
3.2.	PK	PK03: PKPT1	Summary of Pyrimethamine Pharmacokinetic Parameters (non-transformed)		SAC [1]	
3.3.	PK	PK05: PKPT3	Summary of Pyrimethamine Pharmacokinetic Parameters (loge-transformed)		SAC [1]	

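### The Japanese-versus-Caucasian PK comparison in the design rationale is given only plots; an exploratory geometric mean ratio with 95% CI would be a cheap, low-priority addition

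*Protocol*

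**What the plan says.** Protocol 5.4 explains the two-group design partly by a contrast: "comparison of the data in Japanese relative to Caucasian subjects under the same conditions should be beneficial when confirming the relevance" of existing global experience for patients in Japan.

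The objectives contain no contrast. Protocol 4 and SAP 2.2 set PK in Japanese men as primary and PK in Caucasian men as secondary, each with its own endpoints. Protocol 10 tests no hypotheses and states: "An estimation approach will be used to address the PK study objectives", with point estimates and 95% CIs. Protocol 10.3 adds: "These analyses will be performed in each group".

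The between-group view is graphical:

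- Protocol 10.3.2: "An exploratory analysis will be performed using PK parameter plots in order to assess the results in the Japanese and Caucasian subjects".
- SAP 8.3.2: "Plots of AUC(0-t), AUC(0-inf), Cmax and T1/2 versus group (Japanese, Caucasian) will be produced". This is Figure 4.9, which shows the mean with 95% CI by group.
- SAP 10.9.7: Figures 4.10 to 4.13 are individual and mean concentration-time plots labelled for both populations.

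Tables 3.2 and 3.3 summarise the parameters by group. Table 3.3 is the log-scale table; the statistics defined for it include the geometric mean, its 95% CI and the SD of the logs. The SAP synopsis says of the PK data: "No formal statistical analyses will be conducted". SAP 2.1 records: "There were no changes or deviations to the originally planned statistical analysis specified in the protocol".

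**The concern.** The quantity that describes a comparison of exposure between two populations is the ratio, with an interval for that ratio. The plan supplies two separate group intervals and leaves the contrast to the eye. Separate intervals do not directly give the uncertainty of the ratio, and with 6 men per group that uncertainty is considerable, above all for AUC(0-inf).

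At stake is how clearly the report can speak to the use named in Protocol 5.4, which is judging whether global experience carries over to Japan. If the ratio is not pre-specified, readers who want it must compute it themselves and choose the parameters and variance model after seeing the data.

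**Working it through.** **Inputs.** n = 6 per group and between-subject CVs of 18.1% (Cmax) and 44.6% (AUC(0-inf)), from Protocol 10.1.1. CVs 20% higher, 21.7% and 53.5%, from Protocol 10.1.2. The relation between CV and log-scale SD is in SAP 10.4.3. The CVs come from Japanese data only; applying them to Caucasians is an assumption.

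**Log-scale SD.** SD = √ln(1 + CV²), giving 0.1795 for Cmax and 0.4259 for AUC(0-inf).

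**Step 1: reproduce the protocol's per-group figures.** Factor = exp(t × SD/√6), with t(0.975, 5 df) = 2.571.

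- Cmax: exp(2.571 × 0.1795/√6) = 1.207, that is +20.7%. Around 400 this gives 331.3 to 482.9 (protocol: 331.3 to 483.0).
- AUC(0-inf): exp(2.571 × 0.4259/√6) = 1.564, that is +56.4%. Around 40 this gives 25.6 to 62.5 (protocol: the same).

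The stated figures reproduce to rounding.

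**Step 2: the ratio that is not reported.** Pooled variance, factor = exp(t × SD × √(2/6)), with t(0.975, 10 df) = 2.228.

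| Parameter | CV | SD (log) | 95% CI multiplier for the ratio |
|---|---|---|---|
| Cmax | 18.1% | 0.1795 | 0.79 to 1.26 |
| AUC(0-inf) | 44.6% | 0.4259 | 0.58 to 1.73 |
| Cmax, CV +20% | 21.7% | 0.2145 | 0.76 to 1.32 |
| AUC(0-inf), CV +20% | 53.5% | 0.5017 | 0.52 to 1.91 |

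**Step 3: unequal variances.** With equal SDs and equal n, Welch also has 10 df, so it gives the same multipliers. If the Caucasian CV is 0.5 to 1.5 times the Japanese CV (an assumed range), the upper Welch multiplier runs from 1.21 to 1.35 for Cmax and from 1.58 to 1.99 for AUC(0-inf).

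**Step 4: what the outputs would show.** Take the protocol's example geometric means for the Japanese group and an assumed ratio of 1.25.

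| | Japanese (95% CI) | Caucasian (95% CI) | Ratio (95% CI), not planned |
|---|---|---|---|
| Cmax | 400 (331.3 to 482.9) | 320 (265.0 to 386.3) | 1.25 (0.99 to 1.57) |
| AUC(0-inf) | 40 (25.6 to 62.5) | 32 (20.5 to 50.0) | 1.25 (0.72 to 2.16) |

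**Step 5: search of the planned displays.** Tables 3.1 to 3.3, Figures 4.1 to 4.13 and PK Listings 35 and 36 contain concentrations, parameters and per-group summaries. None is specified to show a between-group ratio or an interval for one.

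**The case against.** The plan is consistent with itself. Single-group objectives, no hypotheses, analyses within group and an exploratory graphical view all fit together and look deliberate. The estimation approach in Protocol 10 is tied to the PK objectives, which contain no contrast, so it does not oblige anyone to report a ratio. Protocol 5.4 calls the comparison beneficial; it sets no estimand, similarity margin or decision rule. Side-by-side summaries under the same conditions are a form of comparison. Nothing is lost from the data either: the ratio can be worked out from Table 3.3, and individual parameters are in Listing 36. All of this stands, and it is why the point is low priority.

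The ratio would also be weak evidence. The groups are not randomised (Protocol 7.3), and eligibility sets only a weight floor and a BMI range (Protocol 6.1). The documents give no group weights. As an assumed illustration, a mean weight 10% to 20% higher in Caucasians, with exposure scaling as weight to the power -0.75 to -1, would alone move the ratio to between 1.10^0.75 = 1.07 and 1.20^1 = 1.20. That is a limitation, but it applies equally to the planned plots.

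Three stronger readings are tempting, and the documents support none of them:

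- **That an objective goes unmet.** The per-group estimates with 95% CIs answer both PK objectives.
- **That uncertainty is hidden.** Figure 4.9 shows an interval for each group.
- **That overlapping intervals will be taken as no difference.** At the protocol's CVs, group intervals overlap up to observed ratios of 1.207² = 1.46 (Cmax) and 1.564² = 2.44 (AUC(0-inf)), whereas the ratio's interval excludes 1 beyond 1.26 and 1.73. This would mislead only a reader who applies an overlap rule, and neither document writes one.

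**Conclusion.** The point holds as a cheap improvement of low priority. The rationale names a comparison, the plan assigns only plots to it, and no output states the ratio or its uncertainty. With 6 per group, the interval would be the point ratio times 0.79 to 1.26 for Cmax and 0.58 to 1.73 for AUC(0-inf). These widths assume log-normal data, pooled variance and the Japanese CVs in both groups. The documents give no CV for t1/2, AUC(0-t) or AUC(0-24), so no width is given for those. An AUC interval this wide would not by itself show similarity; reporting it would make the imprecision visible.

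**What to change.** Add to SAP 8.3.2 and to the PK tables (for example as Table 3.4) the Japanese/Caucasian geometric mean ratio with 95% CI for Cmax, AUC(0-t), AUC(0-inf), AUC(0-24) and t1/2. Include t1/2 because it is already plotted by group and because Protocol 5.4 itself quotes it by population: about 107 h in Japanese and 90 h in non-Japanese subjects, a ratio of 107/90 = 1.19.

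- Use a two-sample analysis on the log scale and name the variance assumption in advance, for example Welch with unequal variances.
- Label it exploratory estimation in non-randomised groups, with no hypothesis test.
- Show each group's body weight beside the ratio; Protocol 9.3.1 already has it measured at screening.
- Reword the synopsis line "No formal statistical analyses will be conducted" so that it allows this estimate, and record the addition in SAP 2.1.

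The cost is one table, a few lines of code on data already collected, and two small SAP edits. Objectives, endpoints, sample size and data collection do not change. The downsides are the wide AUC interval and a descriptive ratio that may mix ethnicity with body size; showing weight makes the second visible but does not correct it.

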10.3.3. Interim Analyses

No interim analyses will be planned.

12. APPENDICES

12.1. Appendix 1: Abbreviations and Trademarks

Abbreviations

AE	Adverse event
ALT	Alanine aminotransferase
AST	Aspartate aminotransferase
AUC	Area under the concentration-time curve
AUC(0-24)	Area under the concentration-time curve from time 0 to 24
AUC(0-inf)	Area under the concentration-time curve from time 0 to infinity
AUC(0-t)	Area under the concentration-time curve from time 0 to t
BMI	Body mass index
BUN	Blood urea nitrogen
CFR	Code of Federal Regulations
CI	Confidence intervals
CIOMS	Council for International Organizations of Medical Sciences
CL/F	Apparent clearance following oral dosing
C _{max}	Maximum observed concentration
CONSORT	Consolidated Standards of Reporting Trials
CPK	Creatine phosphokinase
(e)CRF	(electronic) Case report form
CSR	Clinical Study Report
CV	Coefficient of variation
DHFR	Dihydrofolate reductase
ECG	Electrocardiogram
e.g.	exempli gratia
GCP	Good Clinical Practice
GSK	GlaxoSmithKline
h/hr(s)	Hour(s)
HBsAg	Hepatitis B surface antigen
HIPAA	Health Insurance Portability and Accountability Act
HIV	Human Immunodeficiency Virus
HPLC	High performance liquid chromatography
IB	Investigator's Brochure
ICF	Informed Consent Form
ICH	International Conference on Harmonization
i.e.	id est
IEC	Independent Ethics Committees
IgG	Immunoglobulin G
IgM	Immunoglobulin M
INR	International Normalized Ratio
IP	Investigational Product
IUD	Intrauterine device
IUS	Intrauterine hormone-releasing system

kg	Kilogram
LDH	Lactate dehydrogenase
MCH	Mean Corpuscular Hemoglobin
MCV	Mean Corpuscular Volume
mg	Milligram
MHLW	Ministry of Health, Labor and Welfare
mL	Milliliter
MSDS	Material Safety Data Sheet
msec	Millisecond
pH	Pondus Hydrogenii
PK	Pharmacokinetic(s)
PMDA	Pharmaceutical and Medical Devices Agency
QTc	QT interval corrected
QTcF	QT interval corrected for heart rate by Friderician formula
RAP	Reporting and Analysis Plan
RBC	Red Blood Cells
RNA	Ribonucleic acid
SAE	Serious adverse event
SoA	Schedule of Activities
SUSAR	Suspected unexpected serious adverse reactions
t _{1/2}	Terminal half-life
t _{max}	Time to maximum observed concentration
ug	Microgram
ULN	Upper limit of normal
V _d /F	Apparent volume of distribution following oral dosing
WBC	White blood cells
WOCBP	Women of Childbearing Potential

Trademark Information

Trademarks of the GlaxoSmithKline group of companies
DARAPRIM

Trademarks not owned by the GlaxoSmithKline group of companies
Fansidar
WinNonlin
Leucovorin

